## 9.8.2 SECONDARY EFFICACY VARIABLES

---

Progression free survival (PFS) is defined as the time from study entry to the first documentation of tumor progression or death due to any cause whichever comes first. For subjects previously on Arm A of Study UTX-TGR-304, PFS will be calculated from the date of randomization on Study UTX-TGR-304 to the first documentation of tumor progression or death due to any cause whichever comes first. This variable will be analyzed via Kaplan-Meier methodology. The median PFS will be estimated by treatment group, if appropriate (i.e., if sample sizes are sufficient) and overall.

MRD negativity rate is defined as the proportion of subjects who are MRD negative. This variable will be analyzed by the total number and percentage of subjects who are confirmed to achieve MRD negativity as per laboratory confirmation by treatment group and overall.

Duration of response is defined as the time from documentation of a response to treatment to the first documentation of tumor progression or death due to any cause whichever comes first. For subjects previously on Arm A of Study UTX-TGR-304, unless the subject's best overall response during study UTX-TGR-304 was stable disease, the duration of response will be determined from the first documented response on Study UTX-TGR-304. Duration of the response will be summarized using n (sample size), mean, standard deviation, median, minimum and maximum for the responders by treatment group and overall.

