### 1.2 BACKGROUND

---

A Phase 3 randomized study (UTX-TGR-304) to assess the efficacy and safety of ublituximab in combination with TGR-1202 compared to obinutuzumab in combination with chlorambucil in subjects with chronic lymphocytic leukemia (CLL) was launched in September 2015. As part of the study design, subjects from Treatment Arms B, C, and D with disease progression confirmed by the independent review committee (IRC), may be enrolled into this companion study. In addition, at the end of the UTX-TGR-304 study, non-progressed subjects from all treatment arms may also be enrolled to this companion study.

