### 3.1 INCLUSION CRITERIA

---

1. Prior treatment in clinical trial [UTX-TGR-304](#)
  - a. Confirmed progression by IRC on Arms B, C, or D after at least two cycles of treatment in trial UTX-TGR-304. There is no required timeframe to begin treatment on the UTX-TGR-204 protocol; however, if other therapies to treat the disease are implemented in the interim, the subject will not be eligible to enroll in the study.
  - b. Non-progressing subjects on Arm A may be eligible for enrollment when protocol UTX-TGR-304 is completed.
2. Adequate organ system function, defined as follows:
  - a. Absolute neutrophil count (ANC)  $> 750 \times 10^3/\text{mm}^3$  (0.75 K/ $\mu\text{L}$ ) / platelet count  $> 40 \times 10^3/\text{mm}^3$  (40 K/ $\mu\text{L}$ ) unless cytopenias are related to bone marrow involvement.
  - b. Total bilirubin  $\leq 1.5$  times the upper limit of normal (ULN) with the exception of Gilbert's Disease and Autoimmune Hemolytic Anemia.
  - c. Alanine aminotransferase (ALT) and aspartate aminotransferase (AST)  $\leq 2.5 \times$  ULN if no liver involvement or  $\leq 5 \times$  the ULN if known liver involvement
  - d. Calculated creatinine clearance  $> 30$  mL/min (as calculated by the modified Cockcroft-Gault formula).
3. ECOG performance status  $\leq 2$
4. Ability to swallow and retain oral medication
5. Willingness and ability to comply with trial and follow-up procedures, give written informed consent

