### 3.2 EXCLUSION CRITERIA

---

1. Prior treatment with obinutuzumab + chlorambucil (Arm B subjects) or ublituximab (Arm C subjects) within 7 days of Cycle 1/Day 1
2. Subjects refractory to (progressing on) UTX-TGR-304 Treatment Arm A (ublituximab + TGR-1202)
3. Known histological transformation from CLL to an aggressive lymphoma (i.e. Richter's transformation)
4. Evidence of chronic active Hepatitis B defined as Hepatitis B surface antigen positive or Hepatitis B DNA positive by PCR (HBV, NOT including subjects with prior hepatitis B vaccination who are Hepatitis B surface antibody positive only;) or chronic active Hepatitis C infection (HCV) defined as Hepatitis C RNA positive by PCR, cytomegalovirus (CMV) DNA positive by PCR, or known history of HIV. If HBc antibody, HCV antibody or CMV IgG and/or IgM antibody is positive the subject must be evaluated for the presence of HBV, HCV, or CMV by PCR - See [Appendix D](#).
5. Evidence of ongoing systemic bacterial, fungal or viral infection, except localized fungal infections of skin or nails. NOTE: Subjects may be receiving prophylactic antiviral or antibacterial therapies at investigator discretion. Use of anti-pneumocystis pneumonia prophylaxis is required prior to Cycle 1/Day 1 and for the first 2 cycles. After Cycle 2, is per investigator discretion.
6. Woman who are pregnant or lactating.
7. Live virus vaccines four (4) weeks prior to or during ublituximab therapy.

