#### Treatment Schema for Subjects Crossing over from Arm A:

Subjects who crossover from Treatment Arm A will continue their treatment where they left off at the termination of [protocol UTX-TGR-304](#).

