### 9.3 ANALYSIS POPULATIONS

---

The Intent-to-Treat (ITT) population will consist of all subjects who were enrolled and have at least one post-treatment efficacy measurement. Primary efficacy analyses will be performed based on the ITT population.

The Safety Population will include all subjects who were enrolled and received at least one dose of study drug. All safety assessments including toxicity will be performed on the Safety Population.

The Per-Protocol Population (PP) will consist of all ITT subjects without a major protocol deviation. The criteria for a major protocol deviation will be determined and documented prior to data base lock. Subject exclusion from the PP population will also be determined and documented prior to database lock. Supportive analyses may be performed based on the PP population.

Furthermore, in the analyses/summaries, subjects will be assigned a treatment group based on the treatment they received on study UTX-TGR-304 prior to their entering of this Companion Study as appropriate.

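### Arm A PFS is counted from randomization in the parent trial, but only Arm A subjects still progression-free at its end can be analysed, so the Arm A median is overstated and the overall median mixes two clocks

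*Combined protocol and SAP*

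**What the plan says.** Section 9.8.2 sets two PFS origins. Arms B, C and D are counted from study entry. For Arm A the rule is: "For subjects previously on Arm A of Study UTX-TGR-304, PFS will be calculated from the date of randomization on Study UTX-TGR-304". Both are analysed by Kaplan-Meier, and "The median PFS will be estimated by treatment group, if appropriate (i.e., if sample sizes are sufficient) and overall".

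The entry rules restrict who from Arm A can contribute. Section 3.1 says "Non-progressing subjects on Arm A may be eligible for enrollment when protocol UTX-TGR-304 is completed", and Section 3.2 excludes subjects who progressed on Arm A. Section 9.3 confines efficacy to 204 enrollees: "The Intent-to-Treat (ITT) population will consist of all subjects who were enrolled and have at least one post-treatment efficacy measurement".

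For Arm A subjects who responded in 304, Section 9.8.2 says that "the duration of response will be determined from the first documented response on Study UTX-TGR-304". Duration of response (DOR) is summarized by n, mean, SD, median and range.

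Elsewhere the PFS origin differs. The synopsis uses enrollment. Section 2.2 uses randomization, although 204 does not randomize. Neither has an Arm A rule. The synopsis makes PFS and DOR the primary objectives for Arm A, whereas Sections 2.1 and 9.8.2 treat them as secondary.

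**The concern.** Subjects who progressed or died on Arm A during 304 are in neither the event count nor the risk set in 204. Those who do enter could not have had an event before entry, yet the time up to entry is counted as time at risk. The Kaplan-Meier curve must stay at 100% until the shortest entry lag has passed. This is guaranteed (immortal) time, and it lengthens the median.

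The overall median adds a second fault. It combines months since 304 randomization with months since 204 entry, so it has no common origin and describes no defined population quantity.

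Arm A DOR counted from the first 304 response carries the same guaranteed time. At stake is a published Arm A median that could be read as PFS on the combination from randomization.

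**Working it through.** **Inputs from the documents.** Section 1.2 says that 304 "was launched in September 2015". Version 6.0, dated 22 January 2019, still treats the end of 304 as future. From 1 September 2015 to that date is 40.7 months, so an Arm A subject randomized near launch who enters 204 brings about 40 months of guaranteed time. The documents state no PFS median, so there is no figure to reproduce.

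**Assumptions.** 304 closes 40.7 months after launch. Accrual is uniform over 12, 24 or 40.7 months. True median PFS *m* is 18, 24, 36 or 48 months. PFS is Weibull with shape *k* of 0.8, 1.0 (exponential) or 1.3. That makes 3 × 4 × 3 = 36 scenarios.

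**Formulas.** Let *T* be PFS from 304 randomization, with S(t) = exp[−ln 2 · (t/m)^k], and let *L* be the lag from randomization to 204 entry. A subject enters only if T > L.

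- Median under the plan: solve P(T > t | T > L) = 0.5.
- Median from 204 enrollment: solve P(T − L > t | T > L) = 0.5.

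**Worked example: m = 36, accrual 24 months.** Here *L* is uniform on 16.7 to 40.7 months. For the exponential, the fraction still event-free at entry is

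q = [36 / (24 · ln 2)] · (2^(−16.7/36) − 2^(−40.7/36)) = 2.164 × (0.7250 − 0.4567) = 0.581.

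Beyond the longest lag the selected curve is S(t)/q, so the median is 36 × (1 − log₂ q)^(1/k). For k = 1 this is 36 × 1.784 = 64.2 months.

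| Shape k | q | True median | Median under 9.8.2 | Median from 204 enrollment |
|---|---|---|---|---|
| 0.8 | 0.566 | 36 | 76 | 48 |
| 1.0 | 0.581 | 36 | 64 | 36 |
| 1.3 | 0.601 | 36 | 55 | 27 |

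The last column is a different, conditional quantity. It equals 36 at k = 1 only because the exponential has no memory.

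**Full grid.** The Arm A median is overstated by 24-50 months at shape 0.8, 17-35 at shape 1.0 and 12-27 at shape 1.3, a ratio of 1.2 to 3.4. Simulation of 18 of the scenarios agreed within 0.3 months. A separate simulation with exponential PFS, true medians of 18 to 36 months and other lag ranges gave about 11-12 months too high for lags of 0-24 months, rising to about 32 for lags of 24-40 months.

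**Overall median.** Exponential PFS, 24-month accrual, Arm A true median 36, Arms B-D median 18 from 204 entry:

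| Arm A share | Mixed origins (as planned) | All from 204 enrollment |
|---|---|---|
| 25% | 27 | 21 |
| 50% | 40.5 | 25 |
| 75% | 53 | 30 |

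**Delayed-entry Kaplan-Meier.** In the worked example, with risk sets entered at 204 enrollment, it gives 61.2 / 53.0 / 45.9 months at shapes 0.8 / 1.0 / 1.3. The true medians conditional on T > 16.7 months are 61.8 / 52.7 / 45.8; for the exponential, 16.7 + 36 = 52.7. It therefore recovers PFS given survival to the shortest lag, not the unconditional 36.

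**DOR.** With first response at month 3 and complete follow-up, guaranteed time alone raises the median by roughly 10 to 46 months over the same grid, depending on how response is modelled. Section 9.8.2 gives no censoring rule for DOR, and that can pull the other way, so the net DOR bias is not determined.

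**The case against.** Bias needs a target. The plan never says the Arm A figure estimates PFS for everyone randomized to Arm A, and it states the selection and the origin openly. The figure could be read as total progression-free time among those who continued. The text says only Kaplan-Meier methodology, so delayed entry is not ruled out. No hypothesis is tested, by-arm medians depend on sufficient numbers, and every magnitude rests on assumptions. PFS from 204 enrollment is also conditional, and its origin is set by the calendar. Section 1.2 lets non-progressed subjects from all arms enter, which a pooled Arms B-D median does not address.

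Part of this stands. The upward bias is relative to PFS from randomization. Ordinary Kaplan-Meier is inferred from silence, though it is what a programmer following the text would run. The size is illustrative: the 40-month figure holds only if the first Arm A randomization was near launch, and shorter lags give less. The conflict between Section 1.2 and Sections 3.1 and 4.1 needs reconciling, but it does not rescue the Arm A analysis.

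What does not stand is the transparent conditional reading. No section attaches a conditional label, and the overall median has no coherent reading even on that view. In a descriptive study the estimates are the product.

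**Conclusion.** The concern holds: the rule is wrong as written. The sign follows from the entry criteria and needs no hazard assumption. The size does: 12-50 months over the 36 scenarios, and about 11 months at the low end if lags run only from 0 to 24 months. With the other assumptions fixed, a later closure raises it. The mixed-origin overall median is uninterpretable whatever its size. No error rate is affected, so this should be fixed as a misleading estimate. The weight is greater because the synopsis makes Arm A PFS and DOR primary.

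**What to change.** In Section 9.8.2:

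- Measure Arm A PFS from 204 enrollment. Label it conditional on being progression-free at 304 completion, and state that it does not estimate the regimen's unconditional median. Cycle 1 Day 1 is not a usable origin for Arm A, because "Subjects who crossover from Treatment Arm A will continue their treatment where they left off at the termination of" the parent protocol.
- If PFS from 304 randomization is wanted, analyse all subjects randomized to Arm A using linked 304 data. Alternatively, use delayed-entry Kaplan-Meier with risk sets entered at 204 enrollment, labelled conditional on the shortest entry lag.
- For Arm A DOR, keep first response as the origin but use all 304 Arm A responders or delayed-entry Kaplan-Meier. Otherwise report remaining response duration from 204 enrollment under that name. State a censoring rule.
- Restrict the pooled PFS median to Arms B-D.
- Use 204 enrollment as the PFS origin in the synopsis, Section 2.2 and Section 9.8.2, and reconcile Section 1.2 with Sections 3.1 and 4.1 on who may enter at the end of 304.

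The cost is wording and a re-derived start date. Only the analyses using all randomized Arm A subjects or all 304 Arm A responders need 304 data on subjects who did not enter 204. The downside is a less favourable Arm A figure and a conditional estimate that must be explained.

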#### **Secondary Objective**

- To observe progression-free survival (PFS) and duration of response (DOR)
- To observe the % of subjects that achieve MRD negativity
- To observe the safety of ublituximab in combination with TGR-1202

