## 5 STUDY ASSESSMENTS AND TREATMENT SCHEDULE

The table below lists all of the required assessments that should be performed at each study visit.

TABLE 1: STUDY ASSESSMENT AND TREATMENT SCHEDULE

Cycle (C) = 28 days	Screening 	Cycle 1 				Maintenance 		Cycles 15+ 	End of study	
						Cycles 2 - 6	Cycle 9 & 12			
Procedure \ Days (D)	-28-0	D 1	D 2	D 8	D 15	Day 1	Day 1	Q 3 cycles		
Medical History	X									
Rai Staging	X									
ECOG performance status	X	X			X	X	X	X	X	
Physical examination	X	X		X	X	X	X	X	X	
Vital signs (pulse, BP, temp)	X	X		X	X	X	X	X	X	
BM aspirate/biopsy 	X									
Serum Pregnancy Test 	X									
Urine Pregnancy Test 						X	X	X	X	
Hematology 	X 	X	X	X	X	X	X	X	X	
Serum Chemistry	X 	X		X	X	X	X	X	X	
FISH Panel 	X									
Tumor evaluation 	X	Evaluations are to be obtained during cycles 3, 6 & 12. Following cycle 12, evaluations should occur at least every 12 cycles								
Serology: HCV, HBV, CMV 	X									
CMV Surveillance						X 	X	X 		
MRD 						For subjects in PR or CR beginning at the Cycle 6 response assessment				
Ublituximab 		X	X 	X  5	X 	X	X	Q3 months		
Umbralisib (TGR-1202) Dose		Days 1 - 28 (Daily)								
Adverse events (CTC v4.0)		Throughout the study								X 
Concomitant Medication		Throughout the study								X

 Tests that have already been completed as part of the requirements for UTX-TGR-304 may be used to evaluate eligibility for this companion study

 Treatment Administration +/- 1 day window. Physical Exam, Vital Signs, ECOG PS, Hematology and Serum Chemistry visit days have - 1 day window

 Treatment Administration +/- 3 day window Cycles 2-6. Physical Exam, Vital Signs, ECOG PS, Hematology and Serum Chemistry visit days have a - 3 day window during Cycles 2 through 6. Treatment Administration +/- 7 day window after Cycle 6. Physical Exam, Vital Signs, ECOG PS, Hematology and Serum Chemistry visit days have a - 7 day window for all cycles after cycle 6

 Treatment Administration +/- 7 day window. Physical Exam, Vital Signs, ECOG PS, Hematology and Serum Chemistry visit days have a - 7 day window for all cycles after cycle 6

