 Unilateral bone marrow aspirate and/or biopsy performed at investigator discretion in subjects for whom assessment of extent of CLL involvement and bone marrow cellularity is important. In addition, a post-baseline bone marrow biopsy should be completed to confirm potential CR by radiological assessment.

 For women of child bearing potential, completed within 3 days of Cycle 1 Day 1.

 For women of child bearing potential, completed within 3 days of visit

 Must be obtained prior to ublituximab administration if on day of infusion.

 Must be done within 14 days of cycle 1 day 1

 For del(13q), del(11q), del(17p), and (12) trisomy, t(11:14)

 Scans should be completed approximately 45 days prior to Day 1 of Cycle 1. Radiology assessment should include CT or MRI imaging of chest, abdomen, and pelvis.

 Serum virology to include HBsAg, HbC antibody, HCV antibody and CMV IgG and IgM. If HbC antibody, HCV antibody or CMV IgM is positive, subjects must be evaluated for the presence of active HBV, HCV or CMV by PCR

 Q3 months CMV screening by PCR for all subjects.

 Peripheral blood sample may be analyzed by local lab. For subjects MRD negative by peripheral blood, a bone marrow should be completed to confirm MRD negativity. If a bone marrow is not completed, another peripheral blood sample should be collected to confirm the MRD negativity at least 12 weeks later. MRD should continue to be evaluated for subjects with PR/CR at response assessment intervals until 2 consecutive peripheral blood MRD negative results, or 1 negative peripheral blood MRD and 1 negative bone marrow MRD are observed.

 Subjects who received ublituximab on UNITY-CLL trial (Arm C), will not receive split dosing on Day 1 and 2 of cycle 1. Subjects should receive full dose on Cycle 1, Day 1 and will not receive Day 8, and 15 during Cycle 1.

 If clinically significant adverse event or abnormal result is observed that is not resolved by the end-of treatment visit, continue to monitor and record up through 30 days after study drug discontinuation.

TABLE 2: FOLLOW UP ASSESSMENTS SCHEDULE

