### 5.1.1 LABORATORY EVALUATIONS (LOCAL LAB)

1. Hematologic profile and serum chemistry to include:

Serum Chemistry		
Albumin	Creatinine	SGOT [AST]
Alkaline phosphatase	Glucose	SGPT [ALT]
Bicarbonate/ CO 2	LDH	Sodium
BUN	Magnesium	Total bilirubin
Calcium	Phosphorus	Total Protein
Chloride	Potassium	Uric acid
Hematologic Profile		
Hematocrit	Neutrophils	Platelet count
Hemoglobin	Lymphocytes	
Erythrocyte count	Monocytes	
Absolute neutrophil count	Eosinophils	
Absolute leukocyte count	Basophils	

2. Serum and urine pregnancy tests
3. Baseline bone marrow aspirate/biopsy (if applicable)
4. CLL FISH Panel
5. MRD for subjects in CR or PR beginning at Cycle 6 response assessment
6. Serum Virology to include HBsAG, HBc antibody, HCV antibody, and CMV IgG and IgM. If HBc antibody, HCV antibody or CMV IgM are positive the subject must be evaluated for the presence of active HBV, HCV or CMV by PCR - See [Appendix D](#). For all subjects approximately every 3 months CMV screening by PCR. CMV surveillance will discontinue 30 days after last dose of umbralisib, or as otherwise clinically indicated per investigator discretion.

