### 9.2 GENERAL ANALYSIS CONVENTION

---

The primary objective of this compassionate use study is to allow subjects progressing in Arms B, C, and D of [study UTX-TGR-304](#) to receive, and for subjects previously in Arm A to continue to receive, combination therapy with ublituximab plus umbralisib. As the study is primarily observational, no formal hypothesis testing will be conducted. Continuous data will be described using the following descriptive statistics: n, mean, median, minimum and maximum. Data will be displayed in all listings sorted by treatment group (based on the treatment arm the subject was on in Study 304) and subject number.

When count data are presented, the percentage will be suppressed when the count is zero in order to draw attention to the non-zero counts. A row denoted "Missing" will be included in count tabulations where necessary to account for dropouts and missing values. Unless otherwise specified, the denominator for percentages will be the number of subjects with a non-missing assessment in a given treatment group within the analysis population of interest.

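### The MRD-negativity rate has no stated denominator, so the plan's default divides by tested subjects, mostly responders, and overstates the share of all subjects that the objective asks for

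*Combined protocol and SAP*

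**What the plan says.** All references are to the combined protocol and SAP.

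- **Objective.** Section 2.1 lists as a secondary objective "To observe the % of subjects that achieve MRD negativity". The synopsis has the same objective, but only under the heading for subjects from Arms B, C and D of Study 304.
- **Definition and analysis.** Section 9.8.2: "MRD negativity rate is defined as the proportion of subjects who are MRD negative". It continues: "This variable will be analyzed by the total number and percentage of subjects who are confirmed to achieve MRD negativity", by treatment group and overall. It gives no denominator, no analysis population and no rule for subjects without a result. The synopsis and Section 2.2 repeat the definition and add nothing.
- **Default denominator.** Section 9.2, for cases where nothing else is specified: "the denominator for percentages will be the number of subjects with a non-missing assessment in a given treatment group", taken within the analysis population of interest.
- **Who is tested on treatment.** Table 1 in Section 5, MRD row: "For subjects in PR or CR beginning at the Cycle 6 response assessment". Footnote 14 to that table: "MRD should continue to be evaluated for subjects with PR/CR at response assessment intervals". Section 5.1.1 agrees: "MRD for subjects in CR or PR beginning at Cycle 6 response assessment".
- **Who is tested off treatment.** Table 2 in Section 5 marks MRD for subjects who stopped study treatment without progression and are not on other therapy. It shows no PR/CR limit. MRD is not marked for subjects who stopped for progression or who started other therapy.
- **Efficacy population.** Section 9.3 defines ITT as "all subjects who were enrolled and have at least one post-treatment efficacy measurement".

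**The concern.** Each provision is unremarkable alone. Together they make a missing MRD result depend on outcome. A subject who progresses or dies before the Cycle 6 assessment, or who stays in stable disease on treatment, is not scheduled for a test. Under the Section 9.2 rule that subject then leaves the denominator instead of counting as someone who did not reach MRD negativity.

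The study has no hypothesis test, so the reported percentage is itself the result. A reader who sees an MRD-negativity rate beside the stated objective will take it as a share of the subjects who entered. Prior-304 groups may also differ in the share who respond and are tested. Group percentages would then have different and unstated denominators, and could not be compared as shares of subjects.

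**Working it through.** The plan states no MRD rate, target or power, so there is no figure to reproduce. The check is a ratio.

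**Inputs**

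- N: subjects in the analysis set.
- T: subjects in that set with an MRD result; f = T/N is the share tested.
- x: subjects with confirmed negativity; q = x/T is the rate among those tested.
- The documents give no value of f for this study, so a range is assumed. One marker is the earlier combination study in Section 1.5, where 6 of 9 CLL/SLL subjects reached PR (67%). It is used only to place a point in the range.

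**Formulas**

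- Section 9.2 default: x/T = q.
- All subjects, with untested counted as not negative: x/N = q × f.
- Ratio of the first to the second: N/T = 1/f.

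The ratio is above 1 whenever f < 1. The two rates differ whenever, in addition, x is at least 1.

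**Range, taking q = 30% as an assumed rate among tested subjects**

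| Share tested f | Factor 1/f | Default rule | All subjects (q × f) |
|---|---|---|---|
| 40% | 2.5 | 30% | 12% |
| 50% | 2.0 | 30% | 15% |
| 67% | 1.5 | 30% | 20% |
| 80% | 1.25 | 30% | 24% |
| 90% | 1.11 | 30% | 27% |

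The rows also show the problem for group summaries. Two groups with f = 50% and f = 80% would both be reported at 30%, although 15% of subjects in one and 24% in the other reached negativity.

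**Example in counts (all assumed).** 100 subjects in the analysis set, 60 responders all tested, 20 confirmed negative:

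- default rule: 20/60 = 33%
- all subjects: 20/100 = 20%
- ratio: 100/60 = 1.67, which is 1/0.60.

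**Effect of the population.** ITT already leaves out enrolled subjects with no post-treatment efficacy measurement. If 10 such subjects existed beyond the 100, the rate among all enrolled would be 20/110 = 18.2%. This selection is separate from the missing MRD results and adds to it.

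**The case against.** **The definition may already mean all subjects.** The Section 9.2 default yields to anything specified elsewhere, and Section 9.8.2 speaks of a proportion of subjects. The same section restricts the duration-of-response summary to responders in so many words, so the authors could name a responder subset when they wanted one. This is a fair reading, but it is not explicit. Section 9.8.2 sets no denominator and does not set the default aside, so a programmer following the plan would divide by subjects with a result. Even on the kinder view, two readings give materially different percentages.

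**The gap is disclosed.** Section 9.8.2 asks for the number as well as the percentage, and Section 9.2 provides a row for missing values where needed. A careful reader could rebuild the all-subject rate. That limits the harm but leaves the printed percentage unchanged.

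**The stakes are modest.** This is a secondary, descriptive endpoint in a compassionate-use extension, and no decision rule depends on it. That stands, and it bears on priority.

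**Stronger readings that the documents do not support.** A reader might infer any of the following:

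- *That only responders are ever tested.* Table 2 allows MRD off treatment without a PR/CR limit, so some subjects with stable disease may be tested.
- *That the default rate is always higher.* The two rates are equal if everyone in the set is tested or nobody is negative.
- *That the default rate climbs as fewer responders are sampled, for example 20/48 = 42% if 48 of 60 are tested.* This requires every untested responder to be non-negative. If the 48 are representative, 16 negatives are found and 16/48 = 33%, as before.
- *That untested subjects are known not to be MRD negative.* Their status is unmeasured. Counting them as not negative is a conservative convention.

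**Conclusion.** Wrong as written. Followed literally, Sections 9.2, 9.8.2 and 5 together give a rate among tested, mostly responding, subjects, while the objective asks for a percentage of subjects. The overstatement is a factor of 1/f: from 1.11 at 90% tested to 2.5 at 40% tested, and 1.67 in the example (33% against 20%).

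The conclusion rests on two conditions: that the Section 9.2 default governs because Section 9.8.2 does not displace it, and that some of the analysis set goes untested with at least one subject negative. The factor also takes the all-subject rate with untested subjects counted as not negative. The size for this study is unknown, because the plan assumes neither a response rate nor an MRD rate. A rate among tested subjects is a legitimate quantity if labelled as such, but it is not the one the objective names.

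**What to change.** Add to Section 9.8.2, as an explicit override of the Section 9.2 default:

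> The denominator for the MRD-negativity rate is all treated subjects in each prior-304 treatment group. Subjects not tested, or whose negativity is not confirmed, are counted as not MRD negative. The number tested is shown for each group. The rate among tested subjects is given as a supplementary line labelled as such, with its denominator.

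Two choices need to be made openly:

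- **Population.** All treated subjects is preferable, but it departs from the ITT and efficacy sets in Sections 9.3 and 9.8. If the sponsor keeps ITT for consistency, Section 9.8.2 should name it. The rule for untested subjects is needed either way.
- **Arm A rollovers.** The synopsis sets the MRD objective for Arms B, C and D only, while Section 9.8.2 reports by group and overall. Show Arm A separately and state which groups the overall line covers.

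The cost is a few sentences before database lock, with no new samples or visits. The headline rate will be lower, and conservative when responders go untested. In the example, representative testing of 48 of the 60 responders would find 16 negatives and give 16/100 = 16% instead of 20%. The number tested and the supplementary line let a reader see how much of a low rate reflects incomplete sampling.
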